## 4.5 Safety Evaluation

### 4.5.1 Extent of Exposure

Exposure Daily Dose is defined as the mean value of daily dosages of study drug, that is total dosage taken by a patient divided by number of days the patient participated in the study. The total dosage is defined as sum of the recorded doses in the Study Medication and Dose Change Log for each visit. The number of days patient participated in this study is defined as the period from the first dose date (Day 0) to the last recorded dose date. Descriptive statistics of the exposure daily dose of this study will be presented.

Extent of exposure is defined as the total number of days a patient is exposed to study drug. In calculation, the extent of exposure equals the total number of days from the first dose date (Day 0) to the last recorded dose date. If a patient is lost to follow-up, but the drug accountability log confirms that the patient has taken study drug, the last visit date of the treatment period will be used for calculation of extent of exposure. For better description, extent of exposure (in weeks) will also be categorized ( $\leq 1$ , (1-3], (3-6], (6-9], (9-12], (12-16], (16-20], (20-24], (24-28], (28-32], (32-36],  $>36$ ). Descriptive statistics for extent of exposure categorized by weeks will additionally be presented.

A by-patient listing of detailed exposure daily dose, dose modifications and extent of exposure to study drug will be provided. Any extreme values for both the exposure daily dose and the extent of exposure to study medications will be reported in the listings, in case that happens.

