### 4.3 General Considerations

Study day is defined as the number of days relative to Day 0 (i.e., the start of study treatment in the double-blind study VRX-RET-E22-302), computed as (the date – Day 0 date+1).

Continuous data that are assumed to be normally distributed will be summarized in terms of the mean, standard deviation (SD), median, minimum, maximum and number of observations. Continuous data that are expected to be skewed will be presented in terms of the maximum, upper quartile, median, lower quartile, minimum and number of observations. The minimum and maximum will be reported to the same number of decimal places as the raw data recorded in the database. The mean, SD, median, lower quartile and upper quartile will be reported to one more decimal place than the raw data recorded in the database. In general, the maximum number of decimal places reported shall be four for any summary statistic.

Categorical data will be summarized in terms of the number of patients providing data at the relevant time point (n), frequency counts and percentages. Percentages will be presented to one decimal place. Percentages will not be presented for zero counts. Percentages will be calculated using n as the denominator.

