Probable	Temporal association, other etiologies are possible but unlikely. The event may respond if the study drug is discontinued.
Definite	Established temporal association with administration of the study drug with no other probable cause. The event should resolve when the study drug is discontinued and recur on re-challenge.

The intensity and relationship assessments to study drug are recorded on the AE CRF page.

Treatment-emergent AEs (TEAEs) will be tabulated, i.e., those events which are not present at baseline or worsened in severity following the start of treatment. Any adverse events starting more than 30 days after the last administration of study drug will not be tabulated.

The onset date of an adverse event will be compared to the date of first dose of study medication in this extension study to determine if the adverse event is treatment emergent

or not. Adverse events with an onset date on or after the date of first dose of study medication will be classified as treatment emergent.

The following adverse event summaries will be provided:

- A summary of the number and percentage of patients reporting a treatment emergent adverse event by body system, and preferred term
- A summary of the number and percentage of patients reporting a treatment emergent adverse event by maximum intensity, body system and preferred term
- A summary of the number and percentage of patients reporting a treatment emergent adverse event by relationship to study drug, body system and preferred term
- A summary of the number and percentage of patients reporting a treatment emergent adverse event leading to dose modification by body system and preferred term

For each patient and each adverse event, the worst severity recorded will be attributed and used in the by-severity summaries. Similarly, the worst causality (most related to treatment) will be attributed and used in the by-causality summaries. If severity or causality are missing, the worst case will be assumed.

The date the AE started should be well collected in CRF data. However, in the unlikely case that the AE start date is missing, the AE date will imputed be as follows.

Scenarios			Imputed AE Onset Date
Day	Month	Year	
missing			
If the month and year of the AE are the same as the month and year of the first dose date in the extension, use the day of the first dose date.
 
Otherwise use 1 for day.

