TABLE 11.10 RESPONDER RATE ( $\geq 50\%$  REDUCTION IN MONTHLY TOTAL PARTIAL SEIZURE FREQUENCY) FOR PATIENTS TREATED WITH RETIGABINE FOR AT LEAST 32 MONTHS DURING THE OPEN-LABEL EXTENSION  
TABLE 11.11 RESPONDER RATE ( $\geq 50\%$  REDUCTION IN MONTHLY TOTAL PARTIAL SEIZURE FREQUENCY) FOR PATIENTS TREATED WITH RETIGABINE FOR AT LEAST 36 MONTHS DURING THE OPEN-LABEL EXTENSION

**PROGRAMMING NOTE: EVERY TIMEPOINT SHOULD BE INCLUDED WITHIN THE INDICATED DURATION OF OPEN-LABEL TREATMENT. E.G. MONTHS 1, 3, 6, 9, 12, 16, 20, 24, 28, 32 AND 36 WILL BE PRESENTED IN TABLE 11.11.**

52

CONFIDENTIAL

RM2009/00475/00  
VRX-RET-E22-304

Program Path/sas program name

Run Date:

Valeant Pharmaceuticals North America  
Protocol Number: VRX-RET-E22-304

PAGE X OF X

TABLE 12 PROPORTION OF PATIENTS EXPERIENCING A REDUCTION IN MONTHLY TOTAL PARTIAL SEIZURE FREQUENCY  
SAFETY POPULATION

CATEGORY	RETIGABINE (N=XXX)
REDUCTION CATEGORY	
[-100%, -75%]	xx (xx.x%)
(- 75%, -50%]	xx (xx.x%)
(- 50%, -25%]	xx (xx.x%)
(- 25%, 0%)	xx (xx.x%)
WITHOUT REDUCTION	xx (xx.x%)

53

CONFIDENTIAL

RM2009/00475/00  
VRX-RET-E22-304

Program Path/sas program name

Run Date:

TABLE 13 PROPORTION OF SEIZURE-FREE DAYS  
SAFETY POPULATION

STATISTICS	RETIGABINE (N=XXX)
SEIZURE-FREE DAYS (%)	
N	xxx
MEAN	xxx.x
STD	xxx.xx
MEDIAN	xxx.x
MINIMUM	xxx
MAXIMUM	xxx
REDUCTION CATEGORY	
SEIZURE-FREE [=100%]	xx (xx.x%)
NOT SEIZURE-FREE	xx (xx.x%)
[95%, 100%]	xx (xx.x%)
[75%, 95%]	xx (xx.x%)
[50%, 75%]	xx (xx.x%)
[50%, 25%]	xx (xx.x%)
[0%, 25%]	xx (xx.x%)
NUMBER OF PATIENTS WHO WERE SEIZURE-FREE FOR	
6 MONTHS	xx (xx.x%)
12 MONTHS	xx (xx.x%)

54

CONFIDENTIAL

RM2009/00475/00  
VRX-RET-E22-304

TABLE 14 EXTENT OF EXPOSURE TO STUDY MEDICATION  
 SAFETY POPULATION

STATISTICS	RETIGABINE (N=XXX)
EXTENT OF EXPOSURE (DAYS)	
N	xxx
MEAN	xxx.x
STD	xxx.xx
MEDIAN	xxx.x
MINIMUM	xxx
MAXIMUM	xxx
RETIGABINE EXPOSURE CATEGORY (MONTHS)	
N	xxx (100.0%)
[0, 1]	xxx ( xx.x%)
(1, 3]	xxx ( xx.x%)
(3, 6]	xxx ( xx.x%)
(6, 9]	xxx ( xx.x%)
(9, 12]	xxx ( xx.x%)
(12,16]	xxx ( xx.x%)
(16,20]	xxx ( xx.x%)
(20,24]	xxx ( xx.x%)
(24,28]	xxx ( xx.x%)
(28,32]	xxx ( xx.x%)
(32,36]	xxx ( xx.x%)
>36	
DAILY DOSE OF RETIGABINE EXPOSURE (MG)	
N	xxx
MEAN	xxx.x
STD	xxx.xx
MEDIAN	xxx.x
MINIMUM	xxx
MAXIMUM	xxx

55

CONFIDENTIAL

RM2009/00475/00  
 VRX-RET-E22-304

TABLE 15 NUMBER (%) OF PATIENTS REPORTING TREATMENT-EMERGENT ADVERSE EVENTS  
 SAFETY POPULATION

SYSTEM ORGAN CLASS PREFERRED TERM	RETIGABINE (N=XXX)
ANY ADVERSE EVENT	xxx ( xx.x%)

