**CONFIDENTIAL**

RM2009/00475/00  
VRX-RET-E22-304

---

Program Path/sas program name

Run Date:

---

Filename: 87272\_304\_SAP\_v2\_final

page 93 of 148

LISTING 3 DEMOGRAPHICS AND BASELINE CHARACTERISTICS

PATIENT ID	AGE/GENDER/RACE	CONSENT DATE (STUDY DAY)	BASELINE DATE (DAY 0)	START DATE OF EXTENSION (STUDY DAY)	HEIGHT (cm) / WEIGHT (kg)	BMI (kg/m  )	CLINICAL GLOBAL IMPRESSIONS SEVERITY	DURATION OF ILLNESS (YEARS)	TREATMENT / STUDY DURATION (DAYS)	NUMBER OF BACKGROUND AEDS	COMPLETED STUDY?
------------	-----------------	--------------------------	-----------------------	-------------------------------------	---------------------------	--------------------------	--------------------------------------	-----------------------------	-----------------------------------	---------------------------	------------------

This section contained data from each individual patient, rather than in aggregate. They have been excluded to protect patient privacy. Anonymized data from each patient may be made available subject to an approved research proposal. For further information please see the Patient Level Data section of the Sponsor Clinical Study Register.

95

CONFIDENTIAL

RM2009/00475/00  
 VRX-RET-E22-304

Valeant Pharmaceuticals North America  
Protocol Number: VRX-RET-E22-304

PAGE X OF X

96

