**CONFIDENTIAL**

RM2009/00475/00  
VRX-RET-E22-304

---

Program Path/sas program name

Run Date:

---

Filename: 87272\_304\_SAP\_v2\_final

page 105 of 148

LISTING 9 EXTENT OF EXPOSURE TO STUDY MEDICATION

PATIENT ID	AGE/GENDER/RACE	STUDY VISIT	TREATMENT START DATE	TREATMENT STOP DATE	TOTAL DOSE (MG)	AVERAGE DAILY DOSE OF STUDY MEDICATION (MG/DAY)	EXTENT OF EXPOSURE (DAYS)
------------	-----------------	-------------	----------------------	---------------------	-----------------	---	---------------------------

This section contained data from each individual patient, rather than in aggregate. They have been excluded to protect patient privacy. Anonymized data from each patient may be made available subject to an approved research proposal. For further information please see the Patient Level Data section of the Sponsor Clinical Study Register.

107

CONFIDENTIAL

RM2009/00475/00  
VRX-RET-E22-304

LISTING 10 ADVERSE EVENTS CODING DICTIONARY MAPPING

SYSTEM ORGAN CLASS	PREFERRED TERM	REPORTED TERM
SOC 1	PREFERRED TERM 1	REPORTED TERM 1
	PREFERRED TERM 2	REPORTED TERM 2
	:	REPORTED TERM 1
SOC 2	PREFERRED TERM 1	REPORTED TERM 1
	PREFERRED TERM 2	REPORTED TERM 2
:		REPORTED TERM 1

Valeant Pharmaceuticals North America  
Protocol Number: VRX-RET-E22-304

PAGE X OF X

109

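### SAP 4.5.1 starts exposure and mean daily dose at a Day 0 that SAP 4.3 places in the earlier double-blind study, and it bands exposure in weeks where Table 14 uses months

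*SAP*

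**What the plan says.** SAP 4.5.1 (Extent of Exposure) defines two quantities from one start date.

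- **Mean daily dose** is total dose taken divided by days in the study. That number of days "is defined as the period from the first dose date (Day 0) to the last recorded dose date". The numerator is the sum of doses recorded in the Study Medication and Dose Change Log.
- **Extent of exposure**: "the extent of exposure equals the total number of days from the first dose date (Day 0) to the last recorded dose date".

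The only definition of Day 0 is in SAP 4.3 (General Considerations): "Day 0 (i.e., the start of study treatment in the double-blind study VRX-RET-E22-302". The Listing 3 shell is consistent with it. It shows the baseline date, labelled Day 0, in one column and "START DATE OF EXTENSION (STUDY DAY" in another.

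For the bands, SAP 4.5.1 says that "extent of exposure (in weeks) will also be categorized" and names weeks a second time when it describes the summary. The Table 14 shell has the same eleven cut-points (1, 3, 6, 9, 12, 16, 20, 24, 28, 32, 36) under the heading "RETIGABINE EXPOSURE CATEGORY (MONTHS".

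**The concern.** Study 304 is an open-label extension, and its exposure table should describe time and dose on retigabine in the extension. The label attached to the start date in SAP 4.5.1 points instead to the first dose of Study 302, which could have been placebo. Elsewhere the SAP names the extension when it means it: the treatment-emergence rule in SAP 4.5.2 uses the "date of first dose of study medication in this extension study". Section 4.5.1 does not, and neither Table 14 nor Listing 9 (column "TREATMENT START DATE") has a footnote to settle the matter.

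Table 14 and Listing 9 describe how long, and at what dose, patients were treated in a study whose primary objective is long-term safety and tolerability. A wrong origin hides short exposures in the bands and counts placebo days as study drug. A wrong band unit changes the meaning of every class.

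**Working it through.** The documents state no exposure figure to reproduce, so the check applies the SAP's rules to the stated phase lengths.

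**Inputs**
- Study 302 phases (SAP 1 Introduction): titration 4 weeks, maintenance 12 weeks, transition 4 weeks.
- Study month (SAP Table 1, footnote 2): 30 days. SAP 4.4 uses a 28-day month to standardise seizure rates.
- Dose range in the extension (SAP 3.1): 600 to 1,200 mg/day. The examples use a constant 900 mg/day.
- Earlier extension study (Protocol Amendment 2, 7.4): 18 of 222 patients stopped within 3 months; median treatment 358 days.

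**Lead-in under the literal reading**
- Total: 7 × (4 + 12 + 4) = 140 days, and 140 / 30 = 4.67 months.
- Placebo part for former placebo patients (titration plus maintenance): 7 × (4 + 12) = 112 days.

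**Effect on the month bands**
- The shortest nominal exposure is just over 4.67 months, so [0,1] and (1,3] are empty by construction.
- A patient who stops at 90 extension days has (90 + 140) / 30 = 7.67 months and falls in (6,9] instead of (1,3].
- In the earlier extension the group those two bands should show was 18 / 222 = 8.1%.

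**Effect on mean daily dose**

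If the log holds only Study 304 doses, the reported dose after d extension days is 900 × d / (d + 140).

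| Extension days | Calculation | Reported mg/day | Change from 900 |
|---|---|---|---|
| 30 | 900 × 30 / 170 | 159 | −82.4% |
| 180 | 900 × 180 / 320 | 506 | −43.8% |
| 358 | 900 × 358 / 498 | 647 | −28.1% |
| 1,080 | 900 × 1,080 / 1,220 | 797 | −11.5% |

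The reported value stays below 600 mg/day until d = 600 × 140 / 300 = 280 days.

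If Study 302 doses are also summed, a former 900 mg/day patient shows little or no loss. A former placebo patient contributes nothing for 112 days and then a transition dose x, which is not given day by day and is therefore taken as anywhere from 0 to 900 mg/day: (900 × d + 28 × x) / (d + 140).
- d = 180: 506 to 585 mg/day.
- d = 358: 647 to 698 mg/day.

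**Effect of the band unit, whatever the origin**
- Top class in weeks: 36 × 7 = 252 days, or 8.4 thirty-day months.
- Top class in months: 36 × 30 = 1,080 days (36 × 28 = 1,008 with a 28-day month).
- If durations resemble the earlier extension (median 358 days, above 252), more than half of patients would fall in the top class when it is read in weeks, even when counted from the extension start.

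**The case against.** The best reply is that the intent can be inferred. SAP 4.5.1 speaks of participation in this study and takes doses from a visit-based log. Table 14 labels its rows as retigabine exposure, and its lowest bands could never be filled from a Study 302 origin. Listing 9 has a study-visit column, which suggests start and stop dates by Study 304 visit. The cut-points are the extension's visit months, so weeks reads as a slip, and the only calendar month the SAP defines is 30 days. On this view a stray parenthesis and one wrong unit need tidying and nothing more.

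Most of this is right about intent. It does not remove the conflict: Day 0 is a defined term with one meaning, 4.5.1 uses it twice, and the unit is given as weeks twice. Inferring the right answer from the shells means setting aside the text.

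The reply also limits the consequences, and these limits stand.
- The dose figures depend on which doses are summed. Values as low as 159 mg/day would be conspicuous, and the SAP asks for extreme values to be listed.
- Table 1 still counts every discontinuation, so early stoppers are lost only from the exposure bands.
- No test uses exposure. Efficacy rates use open-label duration, and adverse event percentages use patient counts.
- The 8.1% and 358 days come from another study, and their transfer here is an assumption.

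**Conclusion.** The concern holds. As written, SAP 4.5.1 conflicts with the purpose of the exposure summary through its Day 0 origin, and with the Table 14 shell through its band unit. The firm results are a nominal 140-day lead-in, about 112 days of it placebo for former placebo patients, two empty lower bands in Table 14, and a top class that begins at 252 or 1,080 days.

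The 140 days is derived from planned phase lengths, and actual visit timing will shift it. The fall in mean dose is conditional: it is largest if only Study 304 doses are in the numerator, small or absent for former 900 mg/day patients if Study 302 doses are included, and present in both cases for former placebo patients. The damage is confined to the exposure and dose outputs, but those are central to a long-term safety study. The text should be corrected before the tables are programmed.

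**What to change.** - In both definitions in SAP 4.5.1, replace the Day 0 label with the date of first dose of open-label medication in VRX-RET-E22-304.
- State that the dose numerator is the Study 304 log doses over that same period.
- Change weeks to months in both places and give the month length as 30 days, as in the flow chart, so that the text matches Table 14.
- Footnote the start date in Table 14 and Listing 9.
- If combined Study 302 and 304 retigabine exposure is also wanted, report it as a separate line that excludes placebo days.

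The cost is a few wording edits in one SAP section and two footnotes. The extension start date is already planned for Listing 3, so no new data are needed.

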### 4.5.2 Adverse Events

Adverse events (AEs) are monitored from the start of this extension study (informed consent provided by patient at the Baseline visit) until 30 days after administration of the last dose of study drug (end of study drug taper-off).

The AEs will be coded using the most recent Medical Dictionary for Regulatory Activities (MedDRA), Version 9.1. The number and percentage of patients experiencing at least one adverse event will be summarized overall and by body system and preferred term. In any given body system or preferred term patients will only be counted once. Adverse events will further be categorized and summarized by severity and study drug relationship. If the same event for a patient has two different severities, the worst will be taken.

Abnormal laboratory values do not themselves represent adverse events unless they:

- are indicative of a disease or defect, e.g. reduced hematocrit resulting in anemia;

- necessitate intervention, e.g., administration of packed red blood cells or other therapies; and
- result in dose reduction or permanent discontinuation of the drug product.

Worsening of seizure frequency will not be considered an AE but will be captured in the efficacy analysis. Those patients who discontinue their treatment prematurely either during the double-blind period or choose not to enter the open-label extension study should be tapered off their study treatment gradually and will be closely monitored by scheduled clinic visits for worsening of their seizure frequency during this period.

Adverse events will be graded for intensity. An intensity category of mild, moderate, or severe, is defined as

Mild	Causing no limitation of usual activities; the patient may experience slight discomfort
Moderate	Causing some limitation of usual activities; the patient may experience annoying discomfort
Severe	Causing inability to carry out usual activities; the patient may experience intolerable discomfort or pain.

Adverse events will also be graded, by the investigator, for relationship of the AE to study drug. A relationship to study drug category of not related, possible, probable, definite, is defined as

Not Related	No temporal association and other etiologies are likely the cause
Possible	Temporal association, but other etiologies are likely the cause. However, involvement of the study drug cannot be excluded.
Probable	Temporal association, other etiologies are possible but unlikely. The event may respond if the study drug is discontinued.
Definite	Established temporal association with administration of the study drug with no other probable cause. The event should resolve when the study drug is discontinued and recur on re-challenge.

The intensity and relationship assessments to study drug are recorded on the AE CRF page.

Treatment-emergent AEs (TEAEs) will be tabulated, i.e., those events which are not present at baseline or worsened in severity following the start of treatment. Any adverse events starting more than 30 days after the last administration of study drug will not be tabulated.

The onset date of an adverse event will be compared to the date of first dose of study medication in this extension study to determine if the adverse event is treatment emergent

or not. Adverse events with an onset date on or after the date of first dose of study medication will be classified as treatment emergent.

The following adverse event summaries will be provided:

- A summary of the number and percentage of patients reporting a treatment emergent adverse event by body system, and preferred term
- A summary of the number and percentage of patients reporting a treatment emergent adverse event by maximum intensity, body system and preferred term
- A summary of the number and percentage of patients reporting a treatment emergent adverse event by relationship to study drug, body system and preferred term
- A summary of the number and percentage of patients reporting a treatment emergent adverse event leading to dose modification by body system and preferred term

For each patient and each adverse event, the worst severity recorded will be attributed and used in the by-severity summaries. Similarly, the worst causality (most related to treatment) will be attributed and used in the by-causality summaries. If severity or causality are missing, the worst case will be assumed.

The date the AE started should be well collected in CRF data. However, in the unlikely case that the AE start date is missing, the AE date will imputed be as follows.

Scenarios			Imputed AE Onset Date
Day	Month	Year	
missing			
If the month and year of the AE are the same as the month and year of the first dose date in the extension, use the day of the first dose date.
 
Otherwise use 1 for day.

	missing		
If year of onset of AE is before the year of first dose in the extension, use DEC.
 
If the year of the AE is the same as the year of the first dose date in the extension and the day of the AE is greater or equal to the day of the first dose in the extension, use the month from the first dose date. If the day of the AE is less than the day of the first dose in the extension, use the month of first dose + 1. If the month of the first dose in the

			
extension is DEC, then use month of first dose.
 
If the year of onset of AE is after the year of first dose in the extension, use JAN.

		missing	
If the day and month of the AE is before the day and month of the first dose in the extension, assign the missing year as the year of the first dose date + 1. Otherwise, assign the missing year as the year of the first dose date.

missing	missing		
If year of onset of AE is before the year of first dose in the extension, use 01/07/yyyy.
 
If the year of the AE is the same as the year of the first dose in the extension, use the first dose date.
 
If year of onset of AE is after the year of first dose in the extension, use 01/01/yyyy.

	missing	missing	
If the day of the AE is before the day of the first dose in the extension, assign the missing month as the month of the first dose date + 1 and the year as the year of the first dose date. If the month of the first dose in the extension is DEC, then +1 year and use JAN.
 
If the day of the AE is on or after the date of the first dose in the extension, assign the missing month and year as the month and year of the first dose date.

missing		missing	
If the month of the AE is the same or after the month of the first dose in the extension, then use the day and year from first dose.
 
Otherwise, impute the missing day as 1

			and assign the year of the first dose + 1.
missing	missing	missing	Use the first dose date in the extension.

A by-patient listing of all adverse events (including non-treatment-emergent events) will be provided. This listing will be presented by treatment group and will include: centre, patient identifier, age, sex, race, adverse event (body system, preferred term, reported term), date of onset, date of resolution, duration, severity, seriousness, action taken, outcome and causality.

